11.1.2 Protocol Deviations

All protocol deviations will be entered into the Clinical Trial Management System (CTMS) or other approved format.

Information from the Source Documents will represent the primary source of protocol deviations. Information following site monitoring and other manual reviews will be documented in the site visit reports, follow-up letters, audit documentation, or other manual review and will be recorded and tracked in the CTMS or other approved format. Telecommunications and other verbal communications regarding deviations will be

Data and information contained in this document are considered to constitute trade secrets and confidential commercial information, and the legal protections provided to such trade secrets and confidential information are hereby claimed under the provisions of applicable law. No part of this document may be publicly disclosed without the written consent of Philip Morris Products S.A.

considered and handled as important communication, documented and tracked as protocol deviations, as necessary.

Individual entries for protocol deviations that are recorded in the CTMS, or other approved format, following site monitoring and other manual reviews will be reviewed against the individual data points in the eCRF database but will not be formally reconciled with the eCRF database (e.g., their description or occurrence date). The overall procedure for managing protocol deviations are described in the SOPs of the CRO Data Management Team. All deviations will be reviewed periodically, as determined at study start, to identify trends to improve monitoring and/or potential impact on the statistical analysis.

11.2 Data Handling

All study data will be managed by the Data Management Team at the CRO. The overall procedures for quality assurance of clinical study data are described in the SOPs of the CRO Data Management Team. The Data Management Team at CRO will prepare a DMP, to be reviewed and approved by the Sponsor, prior to the start of the study. This document will describe, in detail, the Data Management related procedures and processes.

All data of all subjects enrolled and screening failures who experience an AE during the study (from time of informed consent to end of the safety follow-up period) will be captured and stored in the study database.

All data collected during the study is property of the Sponsor irrespective of the location of the database and the Data Management CRO.

11.2.1 Data Validation

The data will be validated as defined in the DMP and Data Validation Specifications. Discrepancies will be reported as defined in DMP and Data Validation Plan.

Data queries will be raised for discrepant or missing data. All changes to data will be captured in the database with a comprehensive audit trail.

11.2.2 Coding

Adverse events, medical/surgical history, and prior/concomitant medication will be classified according to the terminology of the latest version of the following Dictionaries, at time of coding the first entry:

Medical history:	Medical Dictionary for Regulatory Activities (MedDRA®)
Adverse events:	MedDRA®
Medications:	WHO Drug Dictionary Enhanced and Anatomical Therapeutic and Chemical classification system
THS 2.2 Menthol device issues and/or malfunctions:	C54451/Medical_Device_Problem_Codes_FDA_CDRH

11.2.3 Database Lock

When all outstanding Data Management issues have been resolved and all validation, quality review, and cleaning activities are complete, the database or selected data is/are declared soft locked. Access to change data in the soft-locked database or to change selected data at this time is limited.

After the data is reviewed by the Sponsor, resolution of all raised queries and QC of the changed data, database, or selected data upon Sponsor approval as applicable, is declared locked.

Any changes to the database after that time can only be made by written agreement between the Sponsor and the Data Management and Statistical Team at the CRO. Any of those changes must be documented in the database log file.

After study completion, the study database will be transferred to the Sponsor in the format specified in the DMP in Clinical Data Interchange Standards Consortium's Study Data Tabulation Model (SDTM) Data Structure Specifications.

12 PLANNED STATISTICAL METHODS

12.1 General Considerations

Full details of the statistical analysis will be given in a Statistical Analysis Plan (SAP). Any changes to the planned statistical methods will be documented in the Clinical Study Report. The statistical evaluation will be performed using SAS®, version 9.2 or later.

12.1.1 Stratification Criteria

For the primary analysis of the BoExp, the following stratification criteria will be used:

1. Sex (male; female).
2. Average daily CC consumption over the last 4 weeks as reported during the Screening.

12.1.2 Definitions for Statistical Data Analysis

Baseline:

In general, baseline will be the last available time-point prior to Day 1, 06:30 AM.

THS 2.2 Menthol users: Subjects switching from mCC to THS 2.2 Menthol whose product use pattern categorization is primarily THS 2.2 Menthol or predominantly THS 2.2 Menthol over a defined period will be considered as THS 2.2 Menthol users during that period.. See Section 12.3 for further details on the product use.

Dual use:

Subjects switching from mCC to THS 2.2 Menthol whose product use pattern categorization is dual mostly THS 2.2 Menthol, dual balanced or dual mostly CC over a defined period will be considered as dual users. See Section 12.3 for further details on the product use.

CC users:

Subjects switching from mCC to THS 2.2 Menthol or subjects continuing to use mCC whose product use pattern categorization is primarily CC or predominantly CC over a defined period will be considered as CC users during that period. See Section 12.3 for further details on the product use.

Smoking abstinence:

Data and information contained in this document are considered to constitute trade secrets and confidential commercial information, and the legal protections provided to such trade secrets and confidential information are hereby claimed under the provisions of applicable law. No part of this document may be publicly disclosed without the written consent of Philip Morris Products S.A.

Smoking abstinence during a defined period is defined as using no tobacco-containing product as reported by the subject on the electronic diary.

12.1.3 Descriptive Statistics

All data will be presented in listings, ordered by product arm and subject, unless otherwise specified.

Descriptive statistics for continuous variables (number of subjects [n], number and percent of subjects with data, mean, standard deviation, median, first and third quartiles, minimum and maximum for continuous data, and the n and absolute and relative [%] frequency for categorical data) will be presented by product arm and overall at each time point, where applicable.

For BoExp, the geometric mean and coefficient of variation will be presented in addition to the mean and standard deviation.

Analyses over time will be descriptive statistics of parameters at each assessment timepoint.

12.1.4 Handling of Missing Values and of Values Outside the Detection Limits

Missing values for the BoExp will be imputed using the last observation carried forward (LOCF) approach.

Values below the lower limit of quantification (LLOQ) will be imputed using 0.5 x LLOQ. For values above the upper limit of quantification (ULOQ), the ULOQ will be used for calculation and reporting in summary tables. The number of values below LLOQ or above ULOQ will be presented in each summary table.

For questionnaire data total scores and domain or subscale scores may use a certain degree of imputation by averaging across individual item scores.

Further details will be provided in the SAP.

12.1.5 Significance Level for Inferential Analysis

Unless stated otherwise, all statistical tests will be two-sided and conducted at the 5% level, and all quoted confidence intervals will be two-sided 95% confidence intervals.

The primary endpoints will be tested using a multiple testing procedure to preserve the overall alpha level by simultaneously testing the endpoints using a closed procedure with each test performed at an alpha level of 5%. This implies that statistical significance is required for all primary endpoints in order to be able to make confirmatory claims about any of the endpoints.

Further details will be provided in the SAP.

12.2 Determination of Sample Size and Power Consideration

The following discussion addresses the ability to demonstrate on Day 5 a reduction of at least 50% on four selected primary BoExps and on Day 90 on a fifth primary BoExp in smokers switching from mCC to THS 2.2 Menthol as compared to smokers continuing to smoke mCC.

Table 19 describes the expected coefficients of variation (CV) and mean ratios (MR) between THS 2.2 Menthol and the two control arms in COHb, 3-HPMA, MHBMA and S-PMA on Day 5 based on data from a controlled, randomized, open-label, 3-arm parallel single-center confinement study to investigate exposure to selected smoke constituents in smokers switching from conventional cigarettes to SMAR cigarettes for 5 days, the (YVD-CS01-EU study (ClinicalTrials.gov: ID: NCT00812279) sponsored by PMI. The mean ratios and coefficients of variations for SMAR/CC are expected to be the same as THS 2.2 Menthol/mCC.

Table 19. Expected Mean Ratios and Coefficients of Variation for THS 2.2 Menthol/mCC

	THS 2.2 Menthol /mCC	THS 2.2 Menthol /SA
	MR (CV)	MR (CV)
COHb	0.40 (0.32)	2.10 (0.20)
3-HPMA	0.30 (0.50)	1.70 (0.33)
MHBMA	0.15 (0.70)	1.00 (0.35)
S-PMA	0.20 (0.70)	1.15 (0.42)

Abbreviations: 3-HPMA = 3-hydroxypropylmercapturic acid; CC = conventional cigarettes; COHb = carboxyhemoglobin; CV = coefficients of variation; MHBMA = monohydroxybutenyl mercaptoic acid; MR = mean ratios; S-PMA = S-phenylmercapturic acid; SA = smoking abstinence; THS 2.2 = Tobacco Heating System 2.2.

Table 20 describes the expected coefficients of variation (CV) and mean ratios (MR) between THS 2.2 Menthol and the the mCC control arm in Total NNAL on Day 90 based on data from a a Philip Morris USA-sponsored randomized, controlled, switching, open-label, parallel-group, single-center study in 90 male and female adult smokers evaluated six biomarkers of tobacco smoke exposure over a 12-week period (Frost-Pineda et al., 2008). The mean ratios and coefficients of variations for EHCJLI /CC are expected to be the same as THS 2.2 Menthol/mCC.

**Table 20. Expected Mean Ratios and Coefficients of Variation for THS 2.2 Menthol/mCC**

THS 2.2 Menthol /mCC	
	MR (CV)
Total NNAL	0.30 (0.60)

Abbreviations: Total NNAL = total 4-(methylnitrosamino)-1-(3-pyridyl)-1-butanol; MR = mean ratios; SA = smoking abstinence; THS 2.2 = Tobacco Heating System 2.2.

Table 21 describes the expected coefficients of variation (CV) and mean ratios (MR) between THS 2.2 Menthol and the mCC control arm in COHb, 3-HPMA, MHBMA and S-PMA based on data from a single-center, open-label, randomized, controlled, 2-arm parallel group study to evaluate the exposure to selected smoke constituents in smoking, healthy subjects switching from conventional cigarettes to THS 2.1 compared to subjects continuing to smoke CC for 5 days, the ZRHX-EX-01 study (ClinicalTrials.gov: ID: NCT01780714) sponsored by PMI. The mean ratios and coefficients of variations for THS 2.1/CC are expected to be the same as THS 2.2 Menthol/mCC.

Table 21. Expected Mean Ratios and Coefficients of Variation for THS 2.2 Menthol/mCC

THS 2.2 Menthol /mCC	
	MR (CV)
COHb	0.44 (0.14)
3-HPMA	0.28 (0.20)
MHBMA	0.11 (0.47)
S-PMA	0.07 (0.50)

Abbreviations: 3-HPMA = 3-hydroxypropylmercapturic acid; CC = conventional cigarettes; COHb = carboxyhemoglobin; CV = coefficients of variation; MHBMA = monohydroxybutenyl mercapturic acid; MR = mean ratios; S-PMA = S-phenylmercapturic acid; THS 2.2 = Tobacco Heating System 2.2.

Based on these two sets of assumptions on the mean ratios and coefficients of variations for the four primary BoExp on day 5, the power to demonstrate a reduction was computed.

The comparison will be run on the per protocol population as defined in Section 12.4.2.

Subjects are expected not to have any reason for exclusion from the per protocol population in the confinement period for THS 2.2 Menthol arm and in ambulatory and confinement condition for the mCC arm.

50% of the subjects are expected to be excluded from the per protocol population in the THS 2.2 Menthol arm in the ambulatory (mostly due to lack of compliance to the randomized product). Thus the expected populations on which the reductions will be assessed as described in Table 22.

Table 22. Sample Size to Assess the Reductions

Sample size to assess the reduction (THS 2.2 Menthol:/mCC)	
COHb	80:40
3-HPMA	80:40
MHBMA	80:40
S-PMA	80:40
Total NNAL	40:40

Table 23 describes the expected power to demonstrate a reduction on all 5 primary BoExps in smokers switching from CC to THS 2.2 Menthol as compared to those continuing to smoke mCC, using one-sided test with 2.5% type I error probability using the assumptions from YVD-CS01-EU and ZRHX-EX-01 given a sample size of 160 smokers (~80 in THS 2.2, ~40 in CC, and ~40 in the SA arm). Therefore subjects will be enrolled into the study until there are 160 smokers in the FAS population.

Table 23. Expected power (YVD-CS01-EU and ZRHX-EX-01 studies assumptions)

Assumptions	Reduction					
	50%	51%	52%	53%	54%	55%
YVD-CS01-EU	94%	88%	81%	70%	56%	38%
ZRHX-EX-01	98%	97%	92%	76%	41%	6%

Power considerations related to secondary endpoints of biological changes:

The sample size is sufficient to obtain 95% confidence intervals for the ratio between (geometrical) mean levels of primary BoExps in THS 2.2 Menthol and SA with upper and

Data and information contained in this document are considered to constitute trade secrets and confidential commercial information, and the legal protections provided to such trade secrets and confidential information are hereby claimed under the provisions of applicable law. No part of this document may be publicly disclosed without the written consent of Philip Morris Products S.A.

lower limits deviating not more than 18% from the point estimates, with an 80% overall probability of achieving the desired precision of estimating the true mean.

This study has 80% power using a one-sided test with 2.5% type I error probability:

- To detect a 0.631 [mL/min/kg] (29%) difference between THS 2.2 Menthol and mCC in CYP1A2 activity, as measured by the caffeine clearance, assuming a standard deviation of 0.564. Effect size and variability are derived from data obtained in the (YVD-CS01-EU study sponsored by PMI.
- To detect a 24.71 [ng/g creatinine] (20%) difference between THS 2.2 Menthol and mCC in 11-DTX-B2, assuming a standard deviation of 43.78, as reported by Saareks et al., 2001. The anticipated effect size of THS 2.2 Menthol is assumed to be about 90% of the effect of smoking cessation reported in the paper by Saareks et al., 2001.

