12.5.4 Confirmatory Analysis

The hypothesis to be tested is that the geometric mean level of the BoExp for THS 2.2 Menthol is lower relative to mCC.

For primary BoExp, the hypothesis will be tested on Day 5 for monohydroxybutenyl-mercapturic acid (MHBMA), 3-hydroxypropylmercapturic acid (3-HPMA), S-phenylmercapturic acid (S-PMA), and carboxyhemoglobin (COHb), and on Day 90 Visit for total 4-(methylnitrosamino)-1-(3-pyridyl)-1-butanol (total NNAL) according to the primary and secondary objectives.

Analysis of BoExp will be conducted on the natural log scale. In order to test the follow hypothesis:

Null hypothesis (H0): $m1 \geq m2$

Alternative hypothesis (H1): $m1 < m2$

Where m_1 and m_2 are the geometric means of the biomarker levels on Day 5 or on Day 90 for THS 2.2 Menthol and mCC respectively.

The transformed BoExp data will be analyzed by means of a generalized linear model using product arm as covariate adjusting for the following baseline information: sex, average cigarette consumption over the previous 4 weeks, and baseline value of endpoint. The test will be declared significant if the contrast THS 2.2 Menthol vs mCC is significant. Estimates of differences between groups will be back-transformed to provide relative effects.

Assumptions of the ANOVA model will be tested. Markedly non-lognormally distributed BoExp data will be transformed or analyzed by appropriate non-parametric methods.

Should more than 20% of the subjects be excluded from the PP, would the above confirmatory analysis be repeated on the Compliant Population.

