**Table 15: Expected Power (YVD-CS01-EU and ZRHX-EX-01 Studies Assumptions)**

Assumptions	Reduction					
	50%	51%	52%	53%	54%	55%
YVD-CS01-EU	94%	88%	81%	70%	56%	38%
ZRHX-EX-01	98%	97%	92%	76%	41%	6%

A total of 160 smokers (80 in THS 2.2 Menthol, 40 in mCC, and 40 in the SA arms) were to be randomized over both sites. However due to the site that terminated due to ICH/GCP non-compliance 219 smokers were randomized, so that the 160 smokers would be recruited at the Tokyo Heart Center, to demonstrate a reduction of at least 50% on all 5 primary BoExp in smokers switching from mCC to THS 2.2 Menthol as compared to those continuing to smoke mCC, using one-sided test with 2.5% type I error probability. The calculation of the sample size was based on the assumption that 50% of the subjects in the THS 2.2 Menthol arm would be using THS 2.2 Menthol exclusively at Day 90.

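### The ZRHX-EX-01 row of the power table (Protocol Table 23, SAP Table 15) does not follow from the inputs printed beside it; the 50% column and the sample size are unaffected

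*Protocol*

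**What the plan says.** Protocol section 12.2 presents Table 23, "Expected power (YVD-CS01-EU and ZRHX-EX-01 studies assumptions", as the "expected power to demonstrate a reduction on all 5 primary BoExps", "using one-sided test with 2.5% type I error probability". SAP section 8 repeats it unchanged as Table 15, "Expected Power (YVD-CS01-EU and ZRHX-EX-01 Studies Assumptions". The disputed row reads "ZRHX-EX-01 98% 97% 92% 76% 41% 6" (per cent, for reductions of 50, 51, 52, 53, 54 and 55%).

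The inputs are printed in the same section. Protocol Table 21 (SAP Table 13) gives the ZRHX-EX-01 mean ratios and coefficients of variation for the four Day 5 markers. Protocol Table 20 (SAP Table 12) gives Total NNAL. Table 22 (SAP Table 14) gives 80:40 subjects for the Day 5 markers and 40:40 for Total NNAL, because "50% of the subjects are expected to be excluded from the per protocol population in the THS 2.2 Menthol arm in the ambulatory". Protocol section 12.5.4 fixes the scale: "Analysis of BoExp will be conducted on the natural log scale". Neither document states the power formula, the software, or how the five endpoints were assumed to depend on one another.

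**The concern.** Success on all five markers cannot be more likely than success on any one of them. Under the ZRHX-EX-01 assumptions COHb is the limiting marker beyond 51%: its assumed ratio of 0.44 lies close to the thresholds of 0.48 to 0.45. At the printed inputs, the stated joint power at 52, 53 and 54% is above the power of COHb alone, which no correlation between endpoints can produce. The stated row also falls more steeply towards 55% than a COHb coefficient of variation near 0.14 allows.

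What is at stake is the reliability of a table that shows how much margin the design has beyond its 50% target. A reader who takes 76% at 53% from it is given a figure that the stated assumptions do not support.

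**Working it through.** **Inputs.** ZRHX-EX-01 mean ratio (CV): COHb 0.44 (0.14), 3-HPMA 0.28 (0.20), MHBMA 0.11 (0.47), S-PMA 0.07 (0.50), all at 80:40. Total NNAL 0.30 (0.60) at 40:40. One-sided 2.5%.

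**Formulas.** Log-scale SD σ = √ln(1 + CV²). Standard error SE = σ·√(1/n₁ + 1/n₂). For a reduction r, noncentrality λ = ln((1 − r)/MR)/SE. Power is the probability that a noncentral t with n₁ + n₂ − 2 degrees of freedom exceeds its 97.5% critical value. Joint power under independence is the product over the five markers. The smallest single-marker power is the ceiling under any dependence.

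**COHb.** σ = √ln(1.0196) = 0.1393; SE = 0.1393 × √(1/80 + 1/40) = 0.02698. At 53%, ln(0.47/0.44) = 0.0660 and λ = 2.445. With critical value 1.980, power is 67.9%.

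**Total NNAL.** σ = √ln(1.36) = 0.5545; SE = 0.5545 × √(1/40 + 1/40) = 0.1240. At 53%, ln(0.47/0.30) = 0.4490 and λ = 3.621. Power is 94.7%.

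**Other three markers.** Power is essentially 100% throughout. Joint power at 53% is therefore 0.679 × 0.947 = 64.3%.

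| Reduction | 50% | 51% | 52% | 53% | 54% | 55% |
|---|---|---|---|---|---|---|
| Printed row | 98 | 97 | 92 | 76 | 41 | 6 |
| COHb alone | 99.7 | 97.7 | 89.2 | 67.9 | 37.2 | 12.8 |
| Total NNAL alone | 98.3 | 97.4 | 96.3 | 94.7 | 92.6 | 89.8 |
| Joint, noncentral t | 97.9 | 95.2 | 85.9 | 64.3 | 34.5 | 11.5 |
| Joint, normal approximation | 98.2 | 95.6 | 86.7 | 65.3 | 35.2 | 11.8 |

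The 50% cell reproduces, and 51% is within 2 points. Beyond that, printed minus computed joint power (t) is +6.1, +11.7, +6.5 and −5.5 points. Against the ceiling set by COHb alone, the excess is 92 − 89.2 = 2.8, 76 − 67.9 = 8.1 and 41 − 37.2 = 3.8 points.

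**Other conventions.** Using the CV directly as the log SD, testing the ratio on the raw scale, and holding Total NNAL at the 50% threshold were each tried. So were allocations of 40:40, 53:53, 60:60, 80:80 and 160:40. None restores the row.

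**Rounding.** I varied COHb MR over 0.435–0.445 and CV over 0.135–0.145, and Total NNAL MR over 0.295–0.305 and CV over 0.595–0.605.

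- Whole row: the smallest achievable maximum miss is about 7 points, under independence or under full dependence.
- 50–54% cells only: COHb 0.438 (0.1355) with NNAL 0.295 (0.595) gives 98.7/97.2/91.1/73.5/43.6%, a largest miss of 2.6 points. The same inputs give 16.2% at 55%, against the printed 6%.

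**Check on the other row.** The same method on Table 19 and Table 20 gives 93.9/89.1/81.6/71.2/58.1/43.6% for YVD-CS01-EU, against the printed 94/88/81/70/56/38%. That row agrees to about 1 point at 50–53%, is 2.1 off at 54%, and is 5.6 off at 55%. Varying inputs within rounding (for example COHb 0.404, CV 0.315) brings every cell within about 2 points.

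**The case against.** The strongest reply is that the ceiling argument holds only at exactly 0.44 (0.14), and those figures are rounded. A COHb ratio of 0.437 with CV 0.135 prints identically and gives COHb alone 94.7/79.2/49.8% at 52/53/54%, above all three printed cells. This stands: within rounding, the excess over COHb alone can disappear, and the 50–54% cells can be matched closely. What rounding cannot do is fit those cells and the 55% cell together. The rejection of the whole row therefore rests heavily on 55%, where the documents understate power.

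It is also fair that the YVD-CS01-EU row shows a miss of similar size and direction at 55% on its printed inputs. Both rows fall faster there than this method predicts, which may point to an undisclosed method or to unrounded inputs.

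Finally, nothing is decided on the 51–55% columns. The SAP already reports 219 smokers randomized, so enrolment could not be affected. This is correct and limits the point to a correction of the record.

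Three stronger readings are tempting and not supported. A reader might infer that the trial is underpowered. Success is defined at 50% (Protocol sections 3.4.1 and 12.5.1, SAP section 5.5.2), that cell reproduces at 98%, and the synopsis target is 80%. A reader might take my recomputed row as the true one, but it depends on independence and on two-decimal inputs. A reader might also conclude that a different CV was used. An unrestricted search comes within 2.3 points near COHb 0.4445 (0.10), which suggests this but does not prove it.

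**Conclusion.** The concern holds. The ZRHX-EX-01 row in both documents does not follow from the inputs stated for it. At face value, the printed joint power exceeds its maximum possible value by about 3, 8 and 4 points at 52, 53 and 54%. Against the independence calculation it is too high by about 6, 12 and 6–7 points (5, 11 and 6 by normal approximation), and too low by 5–6 points at 55%.

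The face-value excess needs no assumption about correlation, only the printed inputs, the log scale and a standard two-sample test. The size of the gap in joint power assumes independent endpoints. The finding that rounding cannot rescue the whole row covers independence and full dependence. The cause cannot be identified from the documents. The YVD-CS01-EU row is acceptable within rounding, with a query on its 55% cell. Importance is low.

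**What to change.** Recompute the ZRHX-EX-01 row from the inputs actually used, check the 55% cell of the YVD-CS01-EU row at the same time, and correct Protocol Table 23 and SAP Table 15 together. Add a sentence giving the test, the dependence assumed between endpoints, and the unrounded mean ratios and coefficients of variation. If the printed inputs are the intended ones and the endpoints are taken as independent, the row becomes about 98/95/86/64/35/12%, so five cells change in each document. If unrounded inputs or another method reproduce the printed row, stating them is enough.

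The cost is a few table cells and one sentence per document, with somewhat less favourable figures at 51–54%. No change to the sample size, the success criterion or the analysis follows.
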